Amendment 2, Version 1.0	20Apr2020	
 - Phase 1b Dose Level changes per new available data - Protocol revisions per Atezolizumab IB v15, July 2019 and Atezolizumab IB v15 Addendum 2, December 2019 - Protocol revisions per NT-I7 IB v5, January 29, 2020 - Administrative corrections 	
Amendment 3, Version 1.0	23Apr2021	
 - Protocol revisions per Atezolizumab IB v17, September 2020 - Protocol revisions per NT-I7 IB v6, February 19, 2021 - Added 2 timepoints for Serum Chemistry in Study Calendar Table - Corrected Chemical formula and Structural formula for NT-I7 - NT-I7 dosing schedule changed from Q3W to Q6W (every other cycle) per new available data - Pharmacokinetic draw schedule modified per new available data - Administrative corrections 	
Amendment 4, Version 1.0	11MAR2022	
 - Protocol revisions per Atezolizumab IB v18, July 2021 and Atezolizumab IB v18 Addendum 1, August 2021 - Changed irRC to iRECIST - Clarification to Exclusion Criteria - Added notes, clarification to current protocol language - Administrative corrections 	
Amendment 5, Version 1.0	19JAN2023	- Updated RP2D to 1200 µg/kg	

		
- Protocol revisions per NT-I7 IB v8.0, 19SEP2022- Protocol revisions per Atezolizumab IB v18, July 2021 and Addendum 1, August 2021- Protocol revisions per Dear Investigator Letters, dated July 27, 2022 and November 21, 2022- Administrative corrections and additions	
--	--	--	--

TABLE OF CONTENTS

TABLE OF CONTENTS.....	6
TABLE OF TABLES	8
1. PROTOCOL SUMMARY.....	9
1.1 Synopsis.....	9
1.2 Schema.....	10
2. INTRODUCTION.....	12
2.1 Study Rationale.....	12
2.2 Background - Study Disease(s).....	13
2.3 Agent(s).....	15
2.4 Overall Risk/Benefit and Ethical Assessment.....	19
3. OBJECTIVES AND ENDPOINTS.....	20
4. PATIENT SELECTION.....	22
4.1 Inclusion Criteria	22
4.2 Exclusion Criteria	25
4.3 Inclusion of Women and Minorities	29
5. STUDY DESIGN.....	30
5.1 Overall Design.....	30
5.2 Dose Escalation (Phase 1b).....	31
5.3 Expansion Phase (Phase 2a).....	34
5.4 Other Procedures: Biopsy (core needle, punch or surgical excision).....	35
5.5 Contraception.....	35
6. STUDY TREATMENT.....	36
6.1 Study Treatments Administration.....	36
6.2 Dose-Limiting Toxicity.....	41
6.3 General Concomitant Medication and Supportive Care Guidelines.....	43
6.4 Duration of Therapy.....	45
6.5 Study Treatment beyond Disease Progression.....	46

Trial Type	Phase 1b/2a, non-randomized 2 arm, open label trial with initial NT-I7 dose escalation phase (phase 1b) followed by a dose expansion phase (phase 2a)
Primary Objective	To evaluate the safety and tolerability of NT-I7 in combination with atezolizumab (Phase 1b), including estimation of the maximum tolerated dose (MTD) and/or the recommended Phase 2 dose (RP2D) Phase 2a: To evaluate the Objective Response Rate (ORR) according to RECIST v1.1 and iRECIST, as determined by the investigator
Secondary Objectives	To evaluate immunogenicity of NT-I7 in combination with atezolizumab To make a preliminary assessment of the anti-tumor activity of NT-I7 in combination with atezolizumab
Exploratory Objectives	To make a preliminary assessment of PK parameters of NT-I7 in combination with atezolizumab To make a preliminary assessment of biomarkers that might act as pharmacodynamic indicators of activity of NT-I7 in combination with atezolizumab To make a preliminary assessment of biomarkers that might act as predictors of anti-tumor activity of NT-I7 in combination with atezolizumab
Dose Escalation Phase (Phase 1b)	NT-I7 will be escalated until a plateau of peripheral T-cell level and tumor infiltration of T-cells is reached or unacceptable toxicities.
End Points	Primary endpoint of safety and tolerability of NT-I7 in combination with atezolizumab and estimation of MTD or RP2D for the combination. Secondary endpoints of immunogenicity of NT-I7, Objective Response Rate (ORR), Disease Control Rate (DCR), Duration of Objective Response (DOR), Progression-Free Survival (PFS) and Overall Survival (OS).
Arm I (Phase 2a)	Anti-PD-1/PD-L1 naïve cSCC and MCC
Arm II (Phase 2a)	Anti-PD-1/PD-L1 relapsed/refractory MCC, cSCC and melanoma

Number of Trial Patients	Approximately 84 patients
Number of Clinical Sites	Approximately 8 clinical research sites are expected to participate in this study
Duration of Participation	Each patient will participate in the trial from the time the Informed Consent Form (ICF) is signed through final protocol-specified contact. The active study will end when the last patient completes the 90-day safety follow up visit, approximately 27 months after enrollment.
Estimated Duration of Trial	Trial is expected to be completed approximately 36 months after the last patient is enrolled.

1.2 Schema

Description of Study

This is a Phase 1b/2a, open-label, multicenter study to evaluate the safety, tolerability and anti-tumor effect of NT-I7 (recombinant human interleukin 7 [rhIL]-7-hybrid Fc [hyFc]) in combination with atezolizumab (MPDL3280A) in patients with anti-PD-1/PD-L1 naïve or relapsed/refractory high-risk skin cancers including cSCC, MCC and melanoma.

This study has been designed to allow for an investigation of MTD or RP2D of NT-I7 in combination with atezolizumab. There are two phases to this study:

[figure not shown]
- Phase 1b, a NT-I7 dose-escalation phase to determine the MTD or RP2D
- Phase 2a, a non-randomized parallel dose expansion phase to confirm the MTD or RP2D in both arms.

Arm I: Anti-PD-1/PD-L1 (checkpoint inhibitors [CPI]) naïve patients with cSCC and MCC

Arm II: Anti-PD-1/PD-L1 relapsed/refractory patients with MCC, cSCC and melanoma

Number of Patients

A total of approximately 84 patients will be enrolled; up to approximately 24 patients will be enrolled in the Phase 1b (3 + 3 dose escalation design will be used), and approximately 60 patients will be enrolled in the Phase 2a (24 patients in Arm I, i.e., 12 patients for each indication, and 36 patients in Arm II, i.e., 12 patients for each indication).

[figure not shown]

*Each cohort includes checkpoint inhibitor (CPI) naïve and relapsed/refractory patients with high-risk skin cancer; n=3 or 6 based on the 3+3 study design

^aNT-I7 Dose Interruption

NT-I7 administration will be skipped when the ALC is higher than 10,000 cells/µL on Day 1 of every other cycle, starting on Cycle 3. Blood draws conducted prior to dosing on Day 1 will determine if NT-I7 should be interrupted for the current cycle.

^bStarting with DL4 (1200 µg/kg), NT-I7 dosing is changed from Q3W to Q6W. Atezolizumab dosing remains the same (Q3W).

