11. Patients who have received treatment with any other investigational agent within 4 weeks prior to Cycle 1, Day 1.
12. Patients who have received treatment and failed therapy with checkpoint inhibition plus a T-cell growth factor, e.g., IL-2 (NTKR-204), IL-15 (ALT-803) or IL-7 (CYT107).
13. Patients who have a history of an immune-related Grade 3 or 4 AE attributed to prior cancer immunotherapy (other than endocrinopathy managed with replacement therapy or asymptomatic elevation of serum amylase or lipase) that resulted in permanent discontinuation of the prior immunotherapeutic agent and/or occurred within 6 months prior to Cycle 1, Day 1.
14. Patients who have not completely recovered from irAEs (i.e., have residual toxicities >Grade 1) related to prior cancer immunotherapy (other than endocrinopathy managed

with replacement therapy or stable vitiligo). Patients treated with corticosteroids for irAEs must demonstrate absence of related signs or symptoms for ≥ 4 weeks following discontinuation of corticosteroids.

Note: Patients with a history of severe hypersensitivity reactions to prior immunotherapy are not allowed.

15. Patients with known primary central nervous system (CNS) malignancy, untreated CNS metastases, or active CNS metastases (progressing or requiring corticosteroids for symptomatic control) are excluded, with the following exceptions:

- Patients with a history of treated CNS metastases may be enrolled, provided all the criteria listed above are met as well as the following:
 - Measurable disease outside the CNS
 - No ongoing requirement for corticosteroids as therapy for CNS metastases, with corticosteroids discontinued for ≥ 2 weeks prior to initiation of study treatment
 - Anticonvulsants at a stable dose are allowed
 - Radiographic demonstration of improvement upon the completion of CNS-directed therapy and no evidence of interim progression between the completion of CNS-directed therapy and the screening radiographic study
 - Screening CNS radiographic study ≥ 4 weeks from completion of radiotherapy.

16. Patients who have leptomeningeal disease.

17. Patients who have uncontrolled tumor-related pain:

- Symptomatic lesions amenable to palliative radiotherapy (e.g., bone metastases or metastases causing nerve impingement) should be treated prior to enrollment

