- Asymptomatic metastatic lesions whose further growth would likely cause functional deficits or intractable pain (e.g., epidural metastasis that is not currently associated with spinal cord compression) should be considered for loco-regional therapy if appropriate prior to enrollment.

18. Patients who have uncontrolled hypercalcemia (>1.5 mmol/L ionized calcium or calcium >12 mg/dL or corrected serum calcium \geq ULN) or symptomatic hypercalcemia requiring continued use of bisphosphonate therapy or denosumab.

Note: Use of bisphosphonate therapy or denosumab specifically to prevent skeletal events and patients who do not have a history of clinically significant hypercalcemia are allowed.

Note: Patients on denosumab must be willing and eligible to receive a bisphosphonate instead of denosumab while on study.

19. Patients who have spinal cord compression not definitively treated with surgery and/or radiation or previously diagnosed and treated spinal cord compression without evidence that disease has been clinically stable for ≥ 2 weeks prior to screening.

Treatment-Specific Exclusion Criteria

20. Patients in Arm I (CPI treatment naïve) with autoimmune disease history, including but not limited to systemic lupus erythematosus, rheumatoid arthritis, inflammatory bowel disease, vascular thrombosis associated with antiphospholipid syndrome, Wegener's granulomatosis, Sjögren's syndrome, Bell's palsy, Guillain-Barré syndrome, multiple sclerosis, vasculitis or glomerulonephritis.
21. Patients in Arm II (CPI refractory/relapsed) with autoimmune disease history, including but not limited to systemic lupus erythematosus, rheumatoid arthritis, inflammatory bowel disease, vascular thrombosis associated with antiphospholipid syndrome, Wegener's granulomatosis, Sjögren's syndrome, Bell's palsy, Guillain-Barre syndrome, multiple sclerosis, vasculitis or glomerulonephritis, with the following caveats:
- Patients with a history of autoimmune hypothyroidism on a stable dose of thyroid-replacement hormone may be eligible.
 - Patients with controlled Type 1 diabetes mellitus on a stable insulin regimen may be eligible.
 - Patients with eczema, psoriasis, lichen simplex chronicus, or vitiligo with dermatologic manifestations only (e.g., no psoriatic arthritis) may be eligible provided all the following conditions are met:
 - Rash must cover less than 10% of body surface area (BSA)

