5.3 Expansion Phase (*Phase 2a*)

Patients enrolled into the trial during the Expansion Phase (*Phase 2a*) will be treated at the RP2D level, determined in Phase I to be 1200 µg/kg IM Q6W, as defined in Section [5.2.2](#).

The Phase 2a is designed to evaluate the anti-tumor effects of NT-I7 in combination with atezolizumab in a total of 60 patients. Twenty-four patients in Arm I, i.e., 12 patients for each indication (cSCC and MCC), and 36 patients in Arm II, i.e., 12 patients for each indication (MCC, cSCC and melanoma), will be enrolled. Enrolled patients will be separated into two arms depending on previous use of anti-PD-1/anti-PD-L1 therapy and cancer type.

Arm I (n=24): Anti-PD-1/PD-L1 naïve patients with cSCC (n=12) and MCC (n=12)

Arm II (n=36): Anti-PD-1/PD-L1 relapsed/refractory patients with MCC (n=12), cSCC (n=12) and melanoma (n=12)

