4.2. General Statistical Methods and Data Handling

4.2.1. General Methods

All output will be incorporated into RTF or PDFs, sorted and labeled according to the International Conference on Harmonisation (ICH) recommendations, and formatted to the appropriate page size(s).

Phase 1b/dose escalation will be presented by dose levels 120 µg/kg, 360 µg/kg, 840 µg/kg, 1200 µg/kg and Total. Phase 2a/dose expansion will be summarized under the 1200 µg/kg dose. Efficacy analysis will analyze two groups of pooled data. The first group will pool 120 µg/kg, 360 µg/kg, and 840 µg/kg doses levels of Phase 1b; and the second group will pool the 1200 µg/kg dose level from both phases.

For categorical variables, summary tabulations of the number and percentage within each category (with a category for missing data) of the parameter will be presented.

Continuous variables will be summarized using mean, standard deviation, median, inter-quartile range (IQR) and range; 95% confidence intervals will be presented where appropriate.

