4.7. Study Treatment

Dose intensities will be summarized based on the Safety Population, with phases 1b and 2a presented separately by dose level/arm. Patients who have completed each cycle will be summarized.

The dose intensity of NT-17 and atezolizumab is defined as:

Total actual dose received /duration of treatment(months); where treatment duration is last dose date – first dose date + 1

Dose intensity will be summarized overall for each product.

Study treatment data will be included in a by-patient listing.

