4.11.1. Adverse Events

Adverse events will be coded using the Medical Dictionary for Regulatory Activities (MedDRA) and displayed in tables and listings using System Organ Class (SOC) and Preferred Term (PT). AE severity will be graded according to the CTCAE v5.0.

Analyses of adverse events will be performed for those events that are considered treatment emergent, where a treatment emergent adverse event (TEAE) is defined as any adverse event with an onset date on or after the administration of study treatment through the end of the study (defined as 30 days after the last dose of study treatment) or any event that was present at baseline but worsened in intensity or was subsequently considered drug-related by the investigator through the end of the study.

The number and percentage of patients with any TEAE will be reported, TEAEs with CTCAE Grade 3 or Higher, TEAEs assessed by the Investigator as related to treatment (definite, probable, or possible relationship), Treatment-related TEAE with Grade 3 or Higher, TEAEs leading to NT-17/atezo Interrupted (also Dose Reduced and Withdrawn), Adverse Events of Special Interest (AESI; as designated by the CRF), Serious TEAEs, Serious Treatment-related TEAE, and TEAEs leading to Death; summarized by SOC and PT. In these tabulations, each patient will contribute only once in each category regardless of the number of events.

No formal hypothesis-testing analysis of adverse events incidence rates will be performed.

All adverse events occurring on study will be listed in by-patient listings.

By-patient listings also will be provided for the following: patient deaths and serious adverse events.

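### Phase 2a is described as confirming the dose in both arms, but the SAP plans no adverse-event summary by arm

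*Protocol*

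**What the plan says.** **Purpose.** Protocol section 1.2 describes "Phase 2a, a non-randomized parallel dose expansion phase to confirm the MTD or RP2D in both arms". Protocol section 5.1 and SAP section 2.1 repeat this.

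**Display rule.** SAP section 4.2.1 states: "Phase 2a/dose expansion will be summarized under the 1200 µg/kg dose". SAP section 4.11.1 says that treatment-emergent adverse events (TEAEs) are "summarized by SOC and PT. In these tabulations, each patient will contribute only once in each category"; it mentions no arm. SAP section 4.2.6 plans no subpopulation analyses, and SAP section 5 puts all phases into one table because the study closed early. Dose intensity is the one display that uses arm: SAP section 4.7 has it "with phases 1b and 2a presented separately by dose level/arm".

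**Eligibility (protocol section 4.2).** Exclusion 20 bars autoimmune history in Arm I, the checkpoint-inhibitor-naïve arm, and lists no exceptions. Exclusion 21 applies the same bar to Arm II but with exceptions. One of them is: "Patients with a history of autoimmune hypothyroidism on a stable dose of thyroid-replacement hormone may be eligible". The others cover controlled type 1 diabetes and limited skin disease. Exclusion 13 removes "Patients who have a history of an immune-related Grade 3 or 4 AE attributed to prior cancer immunotherapy" where the event led to permanent discontinuation of the earlier agent and/or fell within 6 months before Cycle 1 Day 1, with stated exceptions. Exclusion 14 removes patients with unresolved immune-related events. Both are written for all patients, but in practice they bear mainly on Arm II, where everyone has had prior anti-PD-1/PD-L1 treatment.

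**The concern.** Whether a dose holds up in both arms is a question about each arm, and a single 1200 µg/kg heading answers it only if the arms have the same toxicity. The eligibility rules give no ground for assuming so. Arm I meets checkpoint inhibition for the first time and has no autoimmune exceptions. Arm II admits some autoimmune history but has lost certain patients who had severe or unresolved immune events on earlier immunotherapy. These features may pull in opposite directions, and the documents do not say which dominates.

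At the planned sizes the pooled rate is weighted 24/60 = 40% to Arm I and 36/60 = 60% to Arm II. A clear excess in one arm could sit behind an unremarkable pooled figure, and a report could then state that the dose was confirmed in both arms without any table showing it.

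**Working it through.** **Inputs.** Arm I n = 24 and Arm II n = 36 (protocol sections 5.3 and 15.3), so Phase 2a n = 60. The documents give no adverse-event rate by arm, so the counts below are assumptions: 12/60, with 6/60 and 18/60 as a range.

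**Method.** Exact (Clopper-Pearson) 95% CI for x/n: lower limit = Beta quantile at 0.025 with parameters (x, n−x+1); upper limit = Beta quantile at 0.975 with parameters (x+1, n−x).

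**Step 1: reproduce the plan's own figures.** The only numerical justification for Phase 2a concerns response rate, and it is by arm (protocol section 15.3, SAP section 4.1).
- Arm I: 17/24 gives 48.9–87.4%, which excludes 45.25%; 16/24 gives 44.7–84.4%, which does not.
- Arm II: 6/36 gives 6.4–32.8%, which excludes 5%; 5/36 gives 4.7–29.5%, which does not.

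Both stated thresholds reproduce with the exact interval. No safety figure is stated for Phase 2a.

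**Step 2: what a pooled count leaves open.**

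| Pooled count | Possible Arm I | Possible Arm II |
|---|---|---|
| 6/60 (10%) | 0/24 to 6/24 (0–25%) | 0/36 to 6/36 (0–16.7%) |
| 12/60 (20%) | 0/24 to 12/24 (0–50%) | 0/36 to 12/36 (0–33.3%) |
| 18/60 (30%) | 0/24 to 18/24 (0–75%) | 0/36 to 18/36 (0–50%) |

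**Step 3: two opposite patterns behind one line.** The pooled line is 12/60 = 20.0% (10.8–32.3%) in both.

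| Pattern | Arm I | Arm II | Weighted check |
|---|---|---|---|
| Excess in Arm I | 10/24 = 41.7% (22.1–63.4%) | 2/36 = 5.6% (0.7–18.7%) | 0.4 × 41.7 + 0.6 × 5.6 = 20.0 |
| Excess in Arm II | 2/24 = 8.3% (1.0–27.0%) | 10/36 = 27.8% (14.2–45.2%) | 0.4 × 8.3 + 0.6 × 27.8 = 20.0 |

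**Step 4: what arm columns could show at full enrolment.** With zero events the upper 95% limit is 1 − 0.025^(1/n). The chance of seeing at least one case of an event with a true rate of 5% is 1 − 0.95^n.

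| | n = 24 | n = 36 | n = 60 |
|---|---|---|---|
| Upper limit, zero events | 14.2% | 9.7% | 6.0% |
| Chance of at least one case | 70.8% | 84.2% | 95.4% |

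Arm-level precision is modest, and worse if early closure left the arms smaller.

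**The case against.** The strongest reply is that no explicit promise of by-arm safety tables is broken. Protocol Table 2 ties the safety objective to Phase 1b and makes response rate the Phase 2a primary objective. Section 5.3 says Phase 2a is there to evaluate antitumour effect. The by-arm rule in protocol section 15.5.1 covers secondary endpoints, not adverse events; its plainer conflict with the SAP is over immunogenicity, which SAP section 4.10 tabulates by dose and phase. All of this stands and limits the weight of the point. It does not remove the stated purpose, which appears in three places, and the synopsis lists safety and tolerability as a primary endpoint without limiting it to a phase.

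Section 4.11.1 also specifies no columns at all, and the SAP refers to table shells that are not in the available text, so the layout cannot be fully verified. That is fair, but the general rule in section 4.2.1 and the absence of subpopulation analyses in section 4.2.6 both point to no split.

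A reader might infer more than the documents support:
- **That the arms were chosen to differ in toxicity risk.** They are defined by prior anti-PD-1/PD-L1 use and cancer type. A difference in risk is an inference from eligibility, and its direction is unknown.
- **That all Phase 2a safety is pooled, or that tolerability is visible for neither arm.** Dose intensity is by arm, and all adverse events appear in by-patient listings, so counts could be recovered if the listings carry arm. A listing is still not a planned summary.

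**Conclusion.** The point holds as a reporting gap. The plan describes Phase 2a as confirming the dose in both arms and, as written, provides no arm-level adverse-event summary. In the illustration the same pooled 20.0% is compatible with an Arm I rate of 8.3% or 41.7%, and with an Arm II rate of 27.8% or 5.6%. Those counts are assumed and use the planned 24 and 36; the sizes after early closure are not given. Smaller arms widen the intervals but do not make a pooled rate describe either arm.

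It would go too far to read the arm columns as confirming the recommended dose by themselves. The dose-limiting toxicity rules drive Phase 1b escalation only, SAP section 2.3 treats stopping rules as not applicable, and no Phase 2a toxicity threshold is set. The columns are needed for a statement about both arms, but they do not settle it.

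**What to change.** In SAP sections 4.2.1 and 4.11.1, define the Phase 2a columns as Arm I, Arm II and Total for the tables of TEAEs, Grade 3 or higher, related, serious and special-interest events, and events leading to discontinuation. Give n/N throughout, with exact 95% CIs for related Grade 3 or higher TEAEs.

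Keep Phase 1b patients treated at 1200 µg/kg in a separate column. Section 4.2.1 describes pooling them with Phase 2a for efficacy only, while section 4.2.3 calls pooling not applicable, so the safety layout needs to be stated.

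If arm columns are not added, list the omission among the changes in SAP section 5 and make no statement in the study report that the dose was confirmed in both arms.

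The cost is small: two more Phase 2a columns plus the separate Phase 1b column, using an arm variable that section 4.7 already needs. The downside is wider intervals per arm, more so after early closure, and they should be read descriptively.

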2. INTRODUCTION

2.1 Study Rationale

Very few preclinical studies have combined interleukin 7 (IL-7) with programmed cell death protein 1 (PD-1), programmed death-ligand 1 (PD-L1), or CTLA-4 checkpoint blockade. One murine study showed the therapeutic efficacy of concomitant blockade of CTLA-4 and PD-1 relies on interdependence of IL-7 and interferon-gamma (IFN-γ) signaling in T-cells, predicting the exogenous IL-7 will boost the therapeutic efficacy [1](#). Another study of murine sepsis showed that IL-7 reverses immune suppression by increasing lymphocyte proliferation, expression of lymphocyte adhesion molecules, IFN-γ production, and CD28 expression on splenic CD8+ T-cells. Combined treatment with IL-7 and anti-PD-1 produced additive effects on CD28 expression, lymphocyte proliferation, and splenic secretion of IFN-γ [2](#). A recent Science paper [3](#) using the mouse model of chronic lymphocytic choriomeningitis virus (LCMV) infection explored the combined effect of IL-7 and anti-PD-L1 on the development and functionality of exhausted T-cells. Anti-PD-L1 treatment moderately improved IL-7 signaling by increasing CD127 (IL-7Rα) expression on exhausted T-cells and exploited potential pathways to improve checkpoint blockade efficacy by combining with IL-7.

Anti-PD-1 and anti-PD-L1 including atezolizumab can induce remarkable responses in a subset of patients with cancer including skin cancers, yet very few are cured. The mechanisms of

immune escape, including (1) the lack of strong, tumor-specific antigens or epitopes recognized by T-cells, (2) impaired or suppressed antigen presentation machinery including downregulation of major histocompatibility complex on cancer cells, (3) impaired or suppressed cytotoxic T-cell activation, (4) poor infiltration of T-cells into the tumor microenvironment (TME), and (5) increased immunosuppressive cytokines and cells in the TME prevent a large proportion of cancer patients from deriving clinical benefit from anti-PD-1/PD-L1 therapies [4](#). Thus, additional therapies to increase the frequency and depth of responses to anti-PD-1/anti-PD-L1 such as atezolizumab are needed.

The current trial will determine whether:

1. Administration of NT-I7 at a dose known to expand T-cell number and repertoire will; (a) increase the number of tumor-infiltrating T-cells; and (b) thereby increase the efficacy of atezolizumab therapy.
2. Administration of NT-I7 with atezolizumab will result in clinically meaningful increases in objective response rate (ORR), disease control rate (DCR), duration of objective response (DOR), progression-free survival (PFS) and overall survival (OS).
3. Assessment of serial tumor biopsies to quantify NT-I7 - induced increases in T-cell infiltration will explore the effect of NT-I7 in combination with atezolizumab on TME, e.g., persistent myeloid infiltration, or overexpression of indoleamine 2,3-dioxygenase (IDO), arginase and transforming growth factor β (TGF- β).

